1. LIST OF ABBREVIATIONS

2. RESPONSIBLE PARTIES

The Japan Good Post marketing Study Practice officer

Amendment number	Date	Substantial or administrative amendment	Protocol section(s) changed	Reason
Version 5	13 December 2019		7.2.3Planned investigation period 7.6.1Case report forms (CRFs)/Data collection tools (DCTs)/Electronic data record 7.6.4.1Procedures for registration	Change target of CRF collection
Version 4	17 September 2019	Other amendment(s)	6.1.limportant identified risks 9NAME, ADDRESS AND OUTSOURCED OPERATIONS OF THE PERSON WHO WAS CONTRACTED WITH THE OPERATIONS	Revistion of RMP Change of outsourced work

3. AMENDMENTS AND UPDATES

Xeljanz A3921248 NON-INTERVENTIONAL STIJDY PROTOCOL Version 5 (Amended 4), 17 December 2019

Amendment number	Date	Substantial or administrative amendment	Protocol section(s) changed	Reason	
Version 3	17 April, 2019	Other amendment(s)	 7.2.4.2. Distribution management Deleted 7.6Data management 13.2Contact information for the EDC system (in the case of study using EDC) 	Change distribution meshod Improvements of descriptions Change mail addess	
Version 2	01 December, 2018	Other amendment(s)	9NAME, ADDRESS AND OUTSOURCED OPERATIONS OF THE PERSON WHO WAS CONTRACTED WITH THE OPERATIONS	Description revision maintenance accompanying establishment of Pfizer R & D	
Final	25 May, 2018	Other amendment(s)	 6 RESEARCH QUESTION AND OBJECTIVES 7.3 Variables (Table 2) 7.3.1 Background 7.3.2 Pre-dosing observation 7.3.2 Pre-dosing observation 7.3.3 XELJANZ use record 7.3.4.1 Drug therapy 7.3.5 Status of vaccination 7.3.7.1 Clinical laboratory tests 7.3.7.6 Colonoscopy 7.3.10 Status of treatment with XELJANZ 9 NAME, ADDRESS AND OUTSOURCED OPERATIONS OF THE PERSON WHO WAS CONTRACTED WITH THE OPERATIONS 14 REFERENCES 	Action against direction by the authorities Improvements of descriptions Improvements of descriptions Improvements of descriptions Improvements of descriptions Improvements of descriptions Addition of footnotes Improvements of descriptions Improvements of descriptions Improvements of descriptions Improvements of descriptions Improvements of descriptions Improvements of descriptions Improvements of descriptions Improvements of descriptions Improvements of descriptions	
NDA_ Amended 3	17 April, 2018	Other amendment(s)	"7.3.12 Major investigation items" deleted	Direction by the authorities	
NDA_ Amended 2	13 April, 2018	Other amendment(s)	5 RATIONALE AND BACKGROUND 6.1 Safety Specifications	Ordinance revision Change to RMP	

Xeljanz A3921248 NON-INTERVENTIONAL STIJDY PROTOCOL Version 5 (Amended 4), 17 December 2019

Amendment	Date	Substantial or	Protocol section(s) changed	Reason
number	er administrative			
		amendment		
			7.2.1 Registration criteria	Improvements of
				descriptions
			7.2.4.2Distribution	Improvements of
			management	descriptions
			7.2.5 Observation period	Action against PMDA inquiry
			7.3 Variables (schedule)	Action against PMDA inquiry
			7.3.3 XELJANZ use record	Action against PMDA inquiry
			7.3.9 9 Status of pregnancy (female	Action against PMDA inquiry
			patients only)	Action against PMDA
			7.3.10 Status of treatment	inquiry
			with XELJANZ	Action against PMDA
			7.3.11 Adverse events	inquiry
				Improvements of
			7.6 Data management	descriptions Clarification of the
			9 NAME, ADDRESS AND	outsourcing
			OUTSOURCED	contractors
			OPERATIONS OF THE PERSON WHO WAS	
			CONTRACTED WITH	
			THE OPERATIONS	Clarification of
			13 CONTACT	contact information
			INFORMATION	Addition of attached
			14 REFERENCES	documents
NDA	13 February, 2018	Other	6.1 Safety Specifications	Change to RMP
Amended 1	101001001,2010	amendment(s)		
		(-)	7.3.1 Background	Reconsideration of the variables
			7.3.2 Pre-dosing observation	Reconsideration of
			7.2.4 Concernitent themeny for	the variables
			7.3.4 Concomitant therapy for ulcerative colitis	Reconsideration of the variables
			7.3.5 5 Status of vaccination	Addition of an
			7.5.5 5 Status of vaccination	applicable vaccine
			7.3.7.1 Clinical laboratory	Reconsideration of
			tests	the parameters
			7.3.7.6 Colonoscopy	Reconsideration of
			, ier, to coronoboopy	the parameters
			7.3.10 Status of treatment	Reconsideration of
			with XELJANZ	the variables
NDA First	10 May, 2017	ot applicable	Not aoolicable	Not aoolicable

4. MILESTONES

Milestone	Planned date
Start of data collection	May 2018
End of data collection	June 2021
Interim report	At the time of submission of Japan Periodic Safety Report
Final study report	Augast 2022

5. RATIONALE AND BACKGROUND

XELJANZ® Tablets 5 mg (non-proprietary name: tofacitinib citrate) (hereinafter "XELJANZ") is a potent inhibitor of Janus kinase (JAK) created by Pfizer Inc. In Japan, XELJANZ received marketing approval for the indication of "rheumatoid arthritis with inadequate response to existing therapy" in March 2013 and the indication of "induction and maintenance therapy for moderate or severe active ulcerative colitis (limited to cases with inadequate response to existing therapy)" in May 2018.

"XELJANZ® Tablets 5 mg Special Investigation (Investigation of Long-term Use in Patients with Ulcerative Colitis)" (hereinafter "Investigation") will be conducted based on the approval conditions in order to understand the safety and effectiveness of long-term use of XELJANZ in patients with ulcerative colitis in clinical settings. Information obtained in this study shall be used to report Ministry of Health, Labour and Welfare (MHLW), Pharmaceuticals and Medical Devices Agency (PMDA), and Pfizer Inc. which is the corporate parent of marketing authorization holder (or sponsor) of XELJANZ. And also, it shall be used for application of re-examination (including Japan Periodic Safety Report), re-evaluation, preparation of material for proper use information of XELJANZ, publications and activities for information service.

This Study shall be conducted in strict compliance with the "MHLW Ordinance on the Standard for Post-Marketing Studies and Clinical Trials of Medical Products" (MHLW Ordinance No. 171, dated December 20, 2004), the "Enforcement of the MHLW Ordinance on the Standard for Post-marketing Studies and Clinical Trials of Medical Products" (PFSB Notification No. 1220008, dated December 20, 2004), "MHLW Ordinance on the Partially Revision of the MHLW Ordinance on the Standard for Post-marketing Safety Control of Medical Products, Quasi-medical Products, Cosmetics, and Medical Devices and on the Partially Revision of the MHLW Ordinance on the Standard for Post-marketing Studies and Clinical Trials of Medical Product s" (MHLW Ordinance No. 26, dated March 11, 2013), the "Enforcement of the MHLW Ordinance on the Partially Revision of the MHLW Ordinance on the Standard for Post-marketing Safety Control of Medical Products, Quasi-medical Products, Cosmetics, and Medical Devices, and on the Partially Revision of the MHLW Ordinance on the Partially Revision of the MHLW Ordinance on the Standard for Post-marketing Safety Control of Medical Products, Quasi-medical Products, Cosmetics, and Medical Devices, and on the Partially Revision of the MHLW Ordinance on the Standard for Post-marketing Safety Control of Medical Products, Quasi-medical Products, Cosmetics, and Medical Devices, and on the Partially Clinical Trials of Medical Products" (PFSB Notification No. 0311-7, dated March 11, 2013), "MHLW Ordinance on the Partially Revision of the MHLW Ordinance on the Standard for Post-marketing Studies and Clinical Trials of Medical Products" (MHLW Ordinance No. 116, dated October 26, 2017), and "Announcement of the MHLW Ordinance on the Partially Revision of the MHLW Ordinance on the Standard for Post-marketing Studies and Clinical Trials of Medical Products (Regarding the MHLW Ordinance on the Standard for Post-marketing Studies and Clinical Trials of Medical Products (Regarding the MHLW Ordinance on the Standard for Post-Marketing Studies and Clinical Trials of Medical Products (October 26, 2017).

6. RESEARCH QUESTION AND OBJECTIVES

This investigation aims to examine the safety and effectiveness of XELJANZ in post-marketing clinical settings when it is administered chronically to patient s with ulcerative colitis, based on the approval conditions below.

[Approval conditions]

Ulcerative colitis

Due to a very limited number of patients studied in clinical trials in Japan, a Drug Use Investigation in all patients should be conducted after launch until data are collected on a target number of patients to understand the background of patients using XELJANZ and collect data on the safety and effectiveness of

6.1. Safety Specifications

The safety specifications included in the Risk Management Plan of XELJANZ are as shown below.

6.1.1. Important identified risks

- Serious infection (including tuberculosis, pneumonia, Pneumocystis pneumonia, sepsis, and opportunistic infection)
- Herpes zoster
- Neutropenia, lymphopenia, oligochromemia
- Hepatic impairment
- Reactivation of hepatitis B virus
- Gastrointestinal perforation
- Interstitial lung disease
- Venous thrombosis

6.1.2. Important potential risks

- Malignant tumor
- Cardiovascular event
- Rhabdomyolysis, myopathy

6.1.3. Important missing information Not applicable.

7. RESEARCH METHODS

7.1. Study design

This is a multicenter cohort investigation to be conducted in patients with ulcerative colitis treated with XELJANZ in clinical settings.

7.2. Setting

7.2.1. Registration criteria

Patients must meet all of the following inclusion criteria to be eligible for inclusion in the study:

- Patients with ulcerative colitis treated with XELJANZ
- Patients naive to XELJANZ in the treatment of ulcerative colitis

For the "indications" and "dosage and administration" of XELJANZ, refer to the latest package insert of the drug.

7.2.2. Sites for this study

This investigation is planned to be conducted at approximately 500 medical institutions of gastrointestinal medicine or gastrointestinal surgery that satisfy the following requirements.

7.2.2.1. Site requirements

- Sites that are able to cooperate with this investigation
- Sites that are sufficiently capable of taking emergency actions (including those that are capable of such actions in collaboration with other institutions*)
 - *: If the diagnosis and treatment are conducted in collaboration with other institutions, the information on safety measures, procedures of adverse reactions, etc. of XELJANZ must be shared with the sites in collaboration and the cooperation system must be confirmed.

• Sites with physicians who satisfy the investigator requirements below: [Investigator requirements]

- Physicians with sufficient knowledge of XELJANZ (including knowledge of adverse reactions)
- Physicians with experience in treatment of ulcerative colitis
- Physicians who are able to cooperate with this investigation
- Physicians who can have an interview with Sponsor

7.2.3. Planned investigation period

The planned period covered by this study is as follows.

• Investigation period: May 2018 to June 2021

• Registration period: May 2018 to until the approval conditions for all cases investigations are lifted

However, when PMDA has accepted to continuing registration only, it is not necessary to enter new CRF.

7.2.4. Study procedures

7.2.4.1. Study method

This investigation will be conducted with all patients surveillance system that register all patients treated with XELJANZ for ulcerative colitis.

This investigation will study patients who use XELJANZ at contract sites after the date of approval of the dosage and administration for ulcerative colitis.

7.2.4.2. Distribution management

Sponsor, upon confirming the completion of contract for this study, shall set up logistics necessary to deliver XELJANZ to the site.

7.2.5. Observation period

The duration of observation will be 60 weeks (14 months) from the date of treatment commencement (Day 1). However, patients who are treated with XELJANZ for more than 60 weeks after the date of treatment commencement will be continuously followed up until the end of the investigation period * (June 2021). For patients who discontinue XELJANZ, information until the discontinuation will be collected.

*: Date of the last observation before June 2021

This study will be conducted using booklet type CRF. Investigator will complete each booklet of CRFs for each observation period in Table 1. However, for patients who discontinue XELJANZ, information until the discontinuation will be collected.

Name of CRF	Observation period
Booklet 1	Treatment commencement to Week 26 (Month 6) of treatment
Booklet 2	Week 27 (Month 7) to Week 60 (Month 14) of treatment
Booklet 3	Week 61 (Month 15) to end of the investigation period (June 2021)

Table 1. Name of CRF and observation period

7.3. Variable s

This study will be conducted according to the schedule of observation in Table 2. However, when PMDA accepted to continuing the case registration only, the information in 7.3.2 to 7.3.11 does not need to be entered in the new CRF.

Table 2. Schedule of observation

Observation item	Patient registrat ion ¹	Baseline ¹¹	Date of treatment commence ment ¹¹	Week 26 of treatment ¹¹		End of investigation period ¹¹
TD number, gender, age ²						
Planned first day of treatment with	Ĭ					
Confirmation of eligibility for XELJANZ treatment	•					
Confirmation of eligibility for the investigation	•					
Height, body weight 4						
Information on ulcerative colitis						
Status of pregnancy (female patients		•				
Prior treatment for ulcerative colitis		8				
Smoking history Family flistory of malignant tumor including lymphoma)						
XELIANZ use record			/			
Concomitant therapy for ulcerative colitis			·····			·
Status of vaccination ⁵		,,,				-
Status of prophylact ic treatment ⁶ Clinical laboratory tests	·					-
Chest X-ray or chest CT7	, 					 
Tuberculosis screening tests						
Blood pressure	I					
Hepatitis B and C virus tests	1					ļ
Colonoscopy ⁸ Clinical evaluation on effectiveness ⁹					3	
	· · ·	 				
Status of treatment with XELJANZ All adverse events			y-		'	
Malignant tumor and adverse events leading to discontinuation ¹⁰					,. ,.	;;ii
1 2 1 1 1 2 1 1 1 1 1						

1. Record the information in the registration form

2. Age at the time when the treatment of XELJANZ is commenced

3. Date when treatment with the commercial product of XELJANZ is started for patients who participated in clinical trials

- 4. Name and duration of the disease. extent of the lesion, severity. status of refractory ulcerative colitis based on treatment response
- 5. Information on vaccination with herpes zoster vaccine and pneumococcal vaccine from baseline to the date of completion of the observation period (or date of discontinuation)
- 6. Information on prophylactic treatment for tuberculosis. Pneumocystis jiroveci i pneumonia and hepatitis B given from 3 months before commencement of XELJANZ treatment to the date of completion of the observation period (or date of discontinuation)
- 7. lofonnation on chest X-ray and chest CT conducted from 3 months before commencement of XELJANZ treatment to the date of completion of the observation period (or date of discontinuation)
- 8. Information on colonoscopy conducted from 6 months before commencement of XELJANZ treatment to the date of completion of the observation period (or date of discontinuation)
- 9. Frequency of defecation. rectal bleeding. findings of colonoscopy (if conducted), and investigator's global assessment
- 10.For patients who continue treatment beyond Week 60 of treatment.collect information on malignant tumor and adverse events leading to treatment discontinuation that occur at and after Week 61 of treatment
- 11. When PMDA has accepted to continuing registration only, it is not necessary to enter new CRF.

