7.3.7. Tests/clinical laboratory tests

The record of the following tests conducted from baseline to the date of completion of the observation period (or date of XELJANZ discontinuation) should include the status, dates and results (or findings) of the tests. **If** the abnormal change is clinically

significant compared to the baseline value, this information should also be recorded in the adverse event field.

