7.3.7.1. Clinical laboratory tests

Results of the following clinical laboratory tests conducted from baseline (within 1 month before treatment commencement, including the date of treatment commencement*) to the date of completion of the observation period (or date of XELJANZ discontinuation).

1. Hematology White blood cell count, neutrophil, eosinophil, lymphocyte, monocyte, red blood cell count, platelet count, hemoglobin

- 2. Blood chemistry AST (GOT), ALT (GPT), AL-P, LDH, total cholesterol, HDL-C, LDL-C, y-GTP, total bilirubin, triglyceride, serum creatinine, creatine kinase, albumin
- 3. Other tests KL-6, -D-glucan, BUN, fecal calprotectin, CRP

*: Within 3 months before treatment commencement for fecal calprotectin

7.3.7.2.Chest X-ray test or chest CT test

Findings of chest X-ray or chest CT conducted from baseline (within 3 months before treatment commencement, including the date of treatment commencement) to the date of completion of the observation period (or date of XELJANZ discontinuation).

7.3.7.3.Tuberculosis screening tests

Results of the following tests conducted from baseline (within 6 months before treatment commencement, including the date of treatment commencement) to the date of completion of the observation period (or date of XELJANZ discontinuation).

- 1. Interferon *y* release assay (QuantiFERON, T-SPOT)
- 2. Tuberculin skin test
- 7.3.7.4.Blood pressure (systolic/diastolic)

Results of measurements from baseline to the date of completion of the observation period (or date of XELJANZ discontinuation).

7.3.7.5.Hepatitis B and C virus tests

Results of the following tests conducted within 3 months before treatment commencement should be recorded. For patients who are HBV carriers, the status of HBV-DNA test conducted up to the completion of the observation period (or date of XELJANZ discontinuation) should be recorded.

- 1. Hepatitis B virus test: HBs antigen, HBs antibody, HBc antibody, and HBV-DNA test
- 2. Hepatitis C virus test: HCV antibody

7.3.7.6.Colonoscopy

Results of colonoscopy (inflammation site and findings) conducted from 6 months before commencement of XELJANZ treatment to the date of completion of the observation period (or date of XELJANZ discontinuation).

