7.4. Data sources

In this study, the investigators extract the necessary information using medical charts, medical records and other information in accordance with the protocol.

- 7.5. Study size
- 7.5.1. Planned sample size

470 to be collected in the safety analysis set (495 to be registered•)

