7. HANDLING OF MISSING DATA

If the date of the end of the treatment with this drug is missing, the date of the last observation recorded in the CRF entry "Status of the treatment with Xeljanz" will be used instead. Treatment completers whose end-of-treatment date has not been recorded will be handled in a way that the treatment continued until the last observation date.

Similarly, if the date of the end of a drug therapy or non-drug therapy is missing, the date of the last observation will be used instead.

If the severity, action taken, or outcome for an AE is missing, it will be treated as "unknown" when summarizing data.

If an efficacy endpoint was not measured within its visit window (Appendix 1), it will be treated as missing data and no imputation will be done. The partial Mayo score will be treated as missing data unless the stool frequency subscore, rectal bleeding subscore, and physician's global assessment subscore have all been measured. Similarly, the Mayo score will be treated as missing data unless the stool frequency subscore, rectal bleeding subscore, findings of flexible sigmoidoscopy subscore, and physician's global assessment subscore have all been measured.

Cleaning-uncompleted data will be in principle handled as follows:

- Items for which data are missing: For both purposes of summarization and listing, the corresponding data will be treated as missing data (or as "unknown" if they are a categorical variable).
- Items for which data are inconsistent: For both purposes of summarization and listing, the inconsistent data will be treated as missing data. A list of how each set of inconsistent data have been handled will be presented separately.
- No signature: For both purposes of summarization and listing, any record in a CRF with no signature of a contract physician (including when the CRF is signed only by individuals other than contract physicians) will be treated as missing data.

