8.2.4.2. Effectiveness assessment based on the Mayo score

• Proportions of patients who achieved the responses based on the partial Mayo score

The proportion of patients who achieved each response based on the Mayo score (remission, mucosal healing, clinical response, clinical remission, endoscopic response, endoscopic remission, symptomatic remission, or deep remission) will be calculated with its 95% CI for each study visit. The definition of the study visits should follow "10.1. Appendix 1: Details of Data Handling".

The definition of the endpoints based on the Mayo score is shown in Table 2.

Table 2. Endpoints Based on the Mayo Score

| Endpoint | Definition |
|-------------------|---|
| Remission | The patient is called to have achieved remission if they meet all the following criteria: |
| | • Mayo score ≤2 |
| | • All Mayo subscores ≤1 |
| | • Rectal bleeding subscore = 0 |
| Mucosal healing | • Findings of flexible sigmoidoscopy subscore ≤1 |
| Clinical response | The patient is called to have achieved clinical response if they meet all the following |
| | criteria: |
| | • The decrease from baseline in the Mayo score ≥3 and ≥30% |
| | • Rectal bleeding subscore ≤1 or the decrease from baseline in the rectal bleeding |
| | subscore ≥1 |

NIS Protocol A3921248 Statistical Analysis Plan

Table 2. Endpoints Based on the Mayo Score

| Endpoint | Definition |
|--------------------|--|
| Clinical remission | The patient is called to have achieved clinical remission if they meet all the following |
| | criteria: |
| | • Mayo score ≤2 |
| | • All subscores ≤1 |
| Endoscopic | • The decrease from baseline in the findings of flexible sigmoidoscopy subscore ≥1 |
| response | |
| Endoscopic | • Findings of flexible sigmoidoscopy subscore = 0 |
| remission | |
| Symptomatic | The patient is called to have achieved symptomatic remission if they meet all the |
| remission | following criteria: |
| | • Mayo score ≤2 |
| | • All subscores ≤1 |
| | • Rectal bleeding subscore = 0 |
| | • Stool frequency subscore = 0 |
| Deep remission | The patient is called to have achieved deep remission if they meet all the following |
| | criteria: |
| | • Mayo score ≤2 |
| | • All subscores ≤1 |
| | • Rectal bleeding subscore = 0 |
| | • Findings of flexible sigmoidoscopy subscore = 0 |

• Changes in the Mayo score

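### The secondary endoscopic and full-Mayo rates in SAP 8.2.4.2 in effect cover only patients who were scoped in routine care; the denominator is unstated, selection is not examined, and some known failures are set to missing

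*Protocol*

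**What the plan says.** - Protocol 7.3, Table 2 footnote 9, lists the effectiveness items and qualifies the endoscopic one: "findings of colonoscopy (if conducted". Stool frequency, rectal bleeding and the global assessment carry no such condition.
- Protocol 7.4: "the investigators extract the necessary information using medical charts". No endoscopy is mandated.
- Protocol 7.3.7: the record of tests "should include the status, dates and results (or findings) of the tests". Protocol 7.3.7.6 asks for "Results of colonoscopy (inflammation site and findings) conducted from 6 months before commencement". Neither asks why the endoscopy was done.
- SAP 7, on an efficacy endpoint not measured in its window: "it will be treated as missing data and no imputation will be done". It adds that "the Mayo score will be treated as missing data unless the stool frequency subscore, rectal bleeding subscore, findings of flexible sigmoidoscopy subscore" and the global assessment are all available.
- SAP 8.2.4.2: "The proportion of patients who achieved each response based on the Mayo score (remission, mucosal healing, clinical response" and five further endpoints are each given with a 95% CI at each visit. SAP 8.1.3 makes the interval for a proportion exact. No denominator is stated, although SAP 8.2.3.1 does state one for onset timing.
- SAP 5.2 removes only patients with no effectiveness item at all, so unscoped patients stay in the effectiveness set without a value for these endpoints.

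**The concern.** Physicians may scope because a patient is doing badly, or to confirm that a patient is doing well. In either case the scoped patients are not a random part of those on treatment. The exact interval covers sampling error only, and nothing in SAP 8.2.4.2 would show a reader which patients were scoped. Partial Mayo data, which need no endoscopy and bear directly on this, are not used here.

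The missing denominator matters too. If the whole effectiveness set were used, every unscoped patient would count as a failure; if only scoped patients are used, which is what SAP 7 implies, the selection problem arises. At stake is how far the mucosal healing and deep remission rates in the final analysis, which supports re-examination (SAP 3), can be read as rates for treated patients.

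**Working it through.** **1. No plan figure to reproduce.** The documents give no scoping rate, reason for scoping or healing rate. The size below therefore rests on assumptions.

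**2. Selection through symptom status.** Let q be the share of observed patients in partial Mayo remission (assumed 0.4, 0.6, 0.7), with mucosal healing assumed to be 80% in remitters and 30% in others. Let R be the probability of being scoped in remitters divided by that in non-remitters.

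- True rate = 0.8q + 0.3(1 − q), which is 50%, 60% and 65% for the three values of q.
- Weight of remitters among the scoped: w = qR / (qR + 1 − q).
- Error of the crude rate = (0.8 − 0.3)(w − q) = 0.5(w − q).

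Example: q = 0.6, non-remitters scoped twice as often (R = 0.5). Then w = 0.30/0.70 = 0.429 and the error is 0.5 × (0.429 − 0.600) = −8.6 points.

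| Difference in scoping | Non-remitters scoped more | Remitters scoped more |
|---|---|---|
| none | 0 | 0 |
| 1.1-fold | −1.0 to −1.2 | +1.0 to +1.2 |
| 1.25-fold | −2.4 to −2.7 | +2.2 to +2.7 |
| 1.5-fold | −4.6 to −5.0 | +3.9 to +5.0 |
| 2-fold | −7.5 to −8.6 | +6.2 to +8.6 |
| 3-fold | −10.9 to −13.3 | +8.8 to +13.3 |

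The entries are percentage points, ranging over the three values of q. They scale with the assumed healing gap: a 25-point gap would halve them.

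**3. For scale.** If half of the planned 470 were scoped (235) and 40% of them (94) had healed, the exact 95% CI would be 33.7% to 46.6%, about ±6.5 points. A 2-fold difference in scoping gives an error of about that size; a 1.25-fold difference gives less than half of it.

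**4. Known failures set to missing.** SAP Table 2 requires, for Mayo remission, clinical remission, symptomatic remission and deep remission alike, a Mayo score ≤2 with every subscore ≤1. The partial Mayo score is the Mayo score minus the endoscopic subscore, so it is then also ≤2, and its three subscores are ≤1. That is exactly partial Mayo remission in SAP Table 1. So a patient with a complete partial Mayo score who is not in partial Mayo remission fails all four, whatever an endoscopy would have shown. Under SAP 7 that patient is missing if unscoped.

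The effect on these four rates is proportional. With q = 0.6 and R = 0.5, the crude rate is w/q = 0.429/0.600 = 0.71 of the true one; with R = 2, w = 1.2/1.6 = 0.75 and the ratio is 1.25. This assumes that scoped remitters represent unscoped remitters.

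**5. Visit windows.** In SAP Appendix A1.2, Week 8 runs from Day 2 to Day 85. It spans Weeks 2, 4 and 8 and part of Week 12 of A1.1, and Week 16 also differs. From Week 24 the two sets coincide. One patient can therefore have several partial Mayo scores in an early A1.2 window, and any use of them needs a selection rule.

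**The case against.** The affected outputs are secondary and descriptive. The primary endpoint (SAP 6.2 and 8.2.4) and the effectiveness subgroups (SAP 8.2.4.5) use partial Mayo remission, there are no decision rules (SAP 4.2), and faecal calprotectin gives a non-invasive second measure. Recording endoscopy only when it was done is normal in a chart-based, non-interventional study. SAP 8.2.4.3 with 8.1.1 already gives n for each subscore at each visit, so from Week 24 a reader can roughly judge how many were scoped. Moderate selection moves the rate by less than the sampling error already displayed. A standardised rate needs choices that the SAP does not yet contain, and it corrects only for selection through partial Mayo status.

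All of this stands as a limit on the point. It does not remove it: the planned n shows how many were scoped but not whether they differ from the rest, and the loss of known failures depends on no assumption about scoping.

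A reader might also infer that the endoscopic rates reflect ordering habits as much as the drug, or that a trend across visits comes entirely from who was scoped. The documents support neither, since they give no scoping or healing rates. Collection also stops at discontinuation (Protocol 7.2.5), which changes the later-visit population for a separate reason.

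**Conclusion.** The point holds for the secondary endpoints in SAP 8.2.4.2 only. Their rates in effect describe scoped patients. That reading follows from the missing-data rule, because the section states no denominator. Bias is possible in either direction and its size is unknown: under the assumed 80% and 30% healing rates, about 2 to 3 points for a 1.25-fold difference in scoping, 4 to 5 for 1.5-fold, 6 to 9 for 2-fold, up to about 13 for 3-fold, and none with equal scoping. Independently of those assumptions, the plan sets to missing some patients whose failure on the four remission endpoints is already known.

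It would go too far to conclude that the study's effectiveness result is unsound or that endoscopy should have been scheduled. The primary endpoint has no endoscopic component, and the collection rule suits the design. The gap is in the analysis plan.

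**What to change.** In SAP 8.2.4.2, keep the crude rates and add the following.

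1. State the denominator. At each A1.2 visit, tabulate patients scoped over patients with a partial Mayo score in the same window, and partial Mayo remission in scoped versus unscoped patients. For scoped patients use the partial Mayo score nearest the endoscopy; for unscoped patients use the one nearest the nominal visit day.
2. As a sensitivity result for mucosal healing and the four remission endpoints, give the rate standardised to partial Mayo remission status: the rate among scoped patients in each stratum, weighted by that stratum's share of all patients with a partial Mayo score in the window. For the four remission endpoints, count non-remitters as failures. Use a bootstrap 95% CI, since the exact method in SAP 8.1.3 is for a simple proportion. Omit the result where a stratum that has to be estimated has too few scoped patients, with the minimum number set in advance.

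Under the assumptions above with q = 0.6, this gives 0.8 × 0.6 + 0.3 × 0.4 = 60%, the true rate, whatever the scoping ratio.

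The cost is SAP wording and one or two extra tables from data already collected: five endpoints at eight post-baseline A1.2 visits make at most 5 × 8 = 40 standardised rates. The interval will be somewhat wider. The result assumes that scoped patients represent unscoped ones with the same partial Mayo status; selection not captured by that status remains.
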